3.1. General assumptions and baseline conditions

Clinical and statistical significance

All the statistical tests within this study will be performed at a 95% confidence level (threshold value p to confirm statistical significance is 0.05).

3.2. Processing missing data

A method of filling in the missing data based on maximum likelihood estimation (MLE) for the primary endpoint will be applied if needed.

The analysis of the rest of endpoint types and other parameters will be performed only on the basis of the available information without filling in the missing data in view of the short duration of the clinical study.

4. Study participants

4.1. Patient distribution

Upon signing of the informed consent for participation in the study, the subjects undergo screening for up to 7 days. The eligible and ineligible subjects will be randomized into two treatment groups at the ratio of 1:1.

Automated randomization sheets will be generated; randomization will be carried out through an electronic CRF system with a randomization module.

Each randomized patient will receive a unique number for the medicinal product dispensing during the study. The patient's number contains R letter and numbers from 001 to 336. Patients numbering does not depend on the study site and is consecutive. In addition to the number, the system will indicate the treatment group to which the patient is randomized. Randomization will be stratified according to two factors: 1) Sex (men vs. women); 2) Hemoglobin level (80–94 g/L versus 95–110 g/L). The randomization number cannot be changed during the study.

STATISTICAL ANALYSIS PLAN

The medicinal product is given to the patient according to the information about the treatment group received from the CRF system. Study treatment also cannot be changed in the process of the study.

Serious deviations from the Protocol should be reported as soon as possible to the Sponsor by the site staff and/or CRO and Monitor (if they are at the Site).

The Sponsor must be informed of minor protocol deviations within 10 business days but before the start of the next study period or before the start of the bioanalytical/statistical phase.

Sponsor has the right to terminate the study, and the Investigator has the right to stop subjects recruitment at any time. In the case of premature closing of the center/study, all completed as well as unused CRFs (including unused pages of partially completed CRFs) and other documents (excluding documents that must be kept in the center) must be returned to the Sponsor. Study materials can be destroyed only with the consent of the Sponsor.

4.3. Study population

4.3.1. Safety population

All randomized subjects who received at least one dose of the investigational medicinal product and completed at least one safety parameters evaluation visit. As distinct from ITT population, the TS population will be analyzed depending on actually received treatment (not only prescribed) (in case of difference between the prescribed and received therapies).

4.3.2. ITT population receiving treatment

All randomized subjects who received at least one dose of the investigational medicinal product and completed at least one efficacy parameters evaluation visit.

4.3.3. Per protocol set

All randomized subjects who completed participation in the study in accordance with the protocol (have completed the prescribed period of treatment and follow-up without significant deviations from the protocol).

5. Demographics and baseline characteristics

All the data obtained in the groups before the study therapy initiation (demographic, laboratory, instrumental, and physical examinations data, vital signs, etc.) will be compared between the groups to determine the groups' comparability for analysis.

The Fisher's exact test and χ^2 (chi-square) will be used to compare the qualitative and serial data, while the t-test or the Mann–Whitney test will be used for the quantitative data (depending on the quantitative data distribution).

To assess the normality of the distribution, the Shapiro-Wilk test will be applied. In the event that any of the initial data reveal the incomparability of the study groups (statistically significant differences in demographic and other initial data between the groups), the analysis of the efficacy and safety parameters will be additionally performed, together with the primary planned analysis, using multi-factor statistics (ANOVA, ANCOVA, or logistic regression analysis depending on the type of the studied parameter), as adjusted for the initial indicator(s) that vary between the groups.

6. Concomitant therapy

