## 9.1.1 Demographic and other baseline data (group comparability for the analysis)

All the data obtained in the groups before the study therapy initiation (demographic, laboratory, instrumental, and physical examinations data, vital signs, etc.) will be compared between the groups to determine the groups comparability for analysis.

The Fisher's exact test and  $\chi^2$  (chi-square) will be used to compare the qualitative and serial data, while the t-test or the Mann–Whitney test will be used for the quantitative data (depending on the quantitative data distribution).

To assess the normality of the distribution, the Shapiro-Wilk Test will be applied.

In the event that any of the initial data reveal the incomparability of the study groups (statistically significant differences in demographic and other initial data between the groups), the analysis of the efficacy and safety parameters will be additionally performed, together with the primary planned analysis, using multi-factor statistics (ANOVA, ANCOVA or logistic regression analysis depending on the type of the studied parameter), as adjusted for the initial indicator(s) that vary between the groups.

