4.2.6. Study design flowchart

Figure 1. Study design flowchart

Study duration

The total duration of the study will be no more than 12 months, including enrollment (9 months), treatment (3 months), and follow-up (by phone) 14 days after the completion of the active treatment period.

Description of visits

4.2.9.1. Visit 0 (screening, days -7...-1)

Visit objectives:

- Signing of the informed consent;
- Assessment of the inclusion/exclusion criteria;

- Collection of demographic and anthropometric data;
- Collection of medical history data on iron deficiency anemia and significant concomitant diseases;
- Physical examination, blood pressure and heart rate measurement;
- Laboratory tests:
 - Urinalysis [general properties (color, pH, specific gravity, protein) and sediment microscopy];
 - Urine pregnancy test;
 - HIV antibody test, except for subjects who had an HIV test within the last 6 months;
 - Blood biochemistry (total protein, total and conjugated bilirubin, AST, ALT, alkaline phosphatase, creatinine, glucose, CRP);
 - Complete blood count (hemoglobin level, hematocrit, RBC, PLT, WBC, leucogram, ESR);
 - Metabolic parameters of iron (serum ferritin and iron level, transferrin, iron transferrin saturation percentage);
 - Determining blood vitamin B9 (folic acid) and vitamin B12 (cyanocobalamin) levels;
 - Determining blood TSH and T4 levels;
 - Creatinine clearance calculation according to the Cockroft-Gault formula;
- Evaluation of the concomitant therapy; Adverse events registration.

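### Baseline significance tests trigger extra efficacy and safety analyses adjusted for whichever variables were flagged; with 44 variables tested, the trigger will probably fire by chance alone

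*SAP*

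**What the plan says.** SAP section 5 sets the scope of testing widely, arm against arm: "All the data obtained in the groups before the study therapy initiation (demographic, laboratory, instrumental, and physical examinations data, vital signs, etc.) will be compared". It uses Fisher or chi-square tests for qualitative data, and t or Mann-Whitney tests for quantitative data. The threshold comes from SAP 3.1: "threshold value p to confirm statistical significance is 0.05". Protocol 9.4 sets the same level.

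The trigger in the SAP reads "In the event that any of the initial data reveal the incomparability of the study groups (statistically significant differences". Protocol 9.1.1 opens its version in the same words: "In the event that any of the initial data reveal the incomparability of the study groups". One significant variable is enough. When that happens, "the analysis of the efficacy and safety parameters will be additionally performed, together with the primary planned analysis", using ANOVA, ANCOVA or logistic regression, "as adjusted for the initial indicator(s) that vary between the groups".

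Neither document gives a multiplicity rule for the baseline tests, a prognostic criterion for a covariate, a limit on how many enter, or a rule for reading an adjusted result that disagrees with the planned one. SAP section 5 does not say which analysis set is compared.

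The primary endpoint has its own model in protocol 9.1.2 and SAP 8.1: ANCOVA with baseline haemoglobin, treatment, sex, weight and haemoglobin category. For the secondary endpoints, the only pre-specified baseline-adjusted comparison between arms is an ANCOVA for week 12 haemoglobin (protocol 9.1.3; Table 2 of the secondary-endpoint layouts in SAP Appendix 1). The iron parameters are compared by t or Mann-Whitney test and the responder rate by chi-square or Fisher test (protocol 9.1.3, SAP 8.2).

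**The concern.** A baseline p-value is a poor basis for choosing covariates. Screening data are collected before randomisation, so in the groups as randomised a significant difference is expected in about one test in twenty even when allocation worked properly. It does not show that the groups are incomparable. Nor does it show that the variable predicts the outcome, which is what makes adjustment worthwhile.

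The rule therefore adjusts for the wrong things at the wrong times. If baseline ferritin differed at p = 0.06, the ferritin comparison would stay unadjusted. If urine pH differed at p = 0.04, efficacy and safety would be reanalysed with urine pH as a covariate.

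What is at stake is clarity of reporting. A second set of results would probably appear beside the planned ones, with a covariate list known only after the data are seen. For the iron parameters and responder rate this is also the only way a baseline-adjusted comparison can arise. Change scores subtract the baseline value but do not adjust for it.

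**Working it through.** The plan states no probability for the trigger, so there is no figure of its own to reproduce.

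**1. Count the tests.** The baseline variables laid out in SAP Appendix 1 are:

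| Panel | Variables | Number |
|---|---|---|
| Efficacy laboratory (at screening) | Hb, serum iron, transferrin, transferrin saturation, ferritin | 5 |
| Urinalysis (Tables 1-3) | pH, protein, specific gravity, RBC, WBC, colour | 6 |
| Haematology other than Hb (Tables 4-7) | haematocrit, RBC, WBC, lymphocytes (2), neutrophils (4), basophils (2), ESR, platelets, eosinophils (2) | 15 |
| Demographic (Tables 12-14) | weight, age, BMI, height, sex | 5 |
| Biochemistry, thyroid, vitamins (Tables 15-17) | ALT, AST, total protein, total bilirubin, CRP, conjugated bilirubin, creatinine, alkaline phosphatase, T4, B12, creatinine index, TSH, folic acid | 13 |

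5 + 6 + 15 + 5 + 13 = 44. Vital signs are named in SAP section 5 but have no layout. Glucose is in the screening panel ("Blood biochemistry (total protein, total and conjugated bilirubin, AST, ALT, alkaline phosphatase, creatinine, glucose, CRP") but not in the layouts. Including them would raise the count.

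**2. Chance of at least one flag, independent tests.** P = 1 - 0.95^k; expected flags = 0.05k.

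- k = 44: 1 - 0.95^44 = 0.895; expected flags 44 x 0.05 = 2.2.
- k = 42, leaving out Hb and sex because randomisation is stratified on sex and Hb category: 1 - 0.95^42 = 0.884; expected flags 2.1.
- k = 25, an assumed effective number after correlation: 1 - 0.95^25 = 0.723.

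**3. Allow for correlation.** Many variables overlap: absolute and percentage cell counts, haematocrit with RBC, weight with BMI, total with conjugated bilirubin. The documents give no correlations, so these are assumptions. A simulation of 200,000 replicates drew 42 normal test statistics in blocks, with within-block correlations from 0.1 (urinalysis) to 0.8 (related cell counts), and counted |z| > 1.96.

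- Block correlations as assumed: 84.8%.
- All correlations raised by a factor of 1.2: 82.1%.
- All 44 variables equally correlated (100,000 replicates each): 87.8% at 0.1, 83.3% at 0.2, 77.2% at 0.3, 59.2% at 0.5.

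The expected number of flags stays at 2.1-2.2 throughout, because correlation does not change it. A correlation of 0.5 between every pair, such as urine colour with height, is not plausible.

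**4. Effect on a primary result if a flagged covariate is added.** Take 286 completers and a covariate unrelated to outcome that is just significant at baseline.

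- R-squared of the covariate with treatment: about 3.84/288 = 0.013.
- Standard error multiplied by 1/sqrt(1 - 0.013) = 1.007, a rise of about 0.7%.
- Half-width from the plan's inputs: 1.976 x 15 x sqrt(2/143) = 3.5 g/L, so the rise is about 0.02 g/L, with no expected shift in the estimate.

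For a non-prognostic covariate the numerical effect on the primary comparison is negligible.

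**The case against.** The strongest reply is that little depends on this rule. Protocol 9.1.2 and SAP 8.1 make the pre-specified ANCOVA the main method and tie the non-inferiority decision to its confidence interval. The triggered analysis is additional and replaces nothing. Protocol 9.1.3 treats all secondary efficacy analyses as explorative, so no confirmatory claim can rest on either version. All of this stands. A reader might infer that the trigger inflates the type I error of the non-inferiority test, or that the plan leaves open which primary result counts. The documents support neither reading.

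What survives is narrower. No rule covers discordant results, chiefly for secondary and safety endpoints. The labelling is also unclear: SAP 8.2 does not repeat the explorative status, and SAP section 10 says that no exploratory analysis is foreseen.

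A reader might also infer that every baseline difference here must be chance. That goes too far. The trial is open-label, protocol 4.10 lets the investigating physician know the randomisation plan, and the ITT and per-protocol sets are filtered after randomisation. Selection or attrition could create real differences. That does not rescue the trigger, because a p-value cannot separate those causes from chance, and attrition calls for a missing-data analysis.

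Finally, 89.5% is a ceiling for the 44 listed variables, since it assumes independence, and 25 effective tests is an assumption. Both objections are fair; a chance flag is still more likely than not.

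**Conclusion.** The point holds as a minor one. The trigger is likely to fire even when randomisation has worked: 89.5% if the 44 tests are independent, about 82-85% under the assumed within-panel correlations, and 72% with 25 effective tests. About two variables would be flagged on average. Those variables would be picked for imbalance, not for their relation to the outcome.

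The consequence is a probable second set of efficacy and safety results with data-selected covariates and no stated way to read disagreement. The iron parameters and responder rate, meanwhile, have no baseline adjustment unless the trigger fires. The primary decision and its error rate are not directly affected.

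The figures rest on the SAP layouts for the count, on the 0.05 threshold applied to each test, on groups that differ only by chance, and on correlations that the documents do not give.

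**What to change.** - Delete the baseline hypothesis tests and the trigger from SAP section 5 and protocol 9.1.1. Summarise baseline data descriptively by arm.
- Leave the primary ANCOVA covariates as pre-specified, including weight. This change is no reason to alter that model.
- For each secondary efficacy endpoint, pre-specify one adjusted comparison, used whatever imbalance is seen: ANCOVA for haemoglobin and the iron parameters, logistic regression for responder rate. Covariates are the parameter's baseline value (haemoglobin for responder rate), sex and haemoglobin stratum. State that this is the result to be interpreted where an unadjusted test is also shown.

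The cost is mainly administrative. Protocol 10.2 classes changes that may influence statistical methods as significant amendments needing approval. Alternatively, protocol 9.7 allows a justified deviation, listed in a SAP finalised before the final analysis and described in the final report. The baseline layouts lose their p-value rows, and layouts are needed for the adjusted secondary models. The SAP has no layouts for the triggered reruns, so none are saved there. Patient numbers, visits and data collection do not change.

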6.1. Permitted concomitant therapy

Patients will take medications, which they took before the enrollment, for the treatment of concomitant diseases during the study. Women that take oral contraceptives may continue taking them during the study.

It is permitted and recommended to take vitamins (not containing iron), folic acid, and ascorbic acid by medical prescription as well as adhere to a diet with products rich in iron.

It is not recommended to take non-steroidal anti-inflammatory medicinal products groundlessly, including selective inhibitors of cyclooxygenase, but these medicinal products may be prescribed by the Investigator due to medical indications.

6.2. Prohibited concomitant therapy

During the study, the enrolled patients must not take the following products:

• prescribed for iron deficiency anemia:

Pharmacotherapeutic groups	Active substance (INN)	
Vitamin and mineral supplements		
Macro- and microelement supplements		
Vitamins and pseudovitamins	Ascorbic acid	

STATISTICAL ANALYSIS PLAN

	Pyridoxine		
	Riboflavin		
Vitamin and pseudovitamins in combinations	Multivitamins + Minerals		
Macro- and microelements	Iron protein succinylate		
	Hematogen		
Mana and mineral mantain a surlimations	Ferrous sulfate + Serine + Folic acid		
Macro- and microelements in combinations	Multivitamins + Minerals		
	Iron (III) hydroxide polymaltosate complex		
	Iron (III) hydroxide sucrose complex		
	Ferrous gluconate		
	Ferric carboxymaltosate		
Hematopoiesis-stimulating agents	Iron protein succinylate		
	Ferrous sulfate		
	Ferrous fumarate		
	Ferrous chloride		
	Cyanocobalamin		
	Iron (III) hydroxide polymaltosate complex + Folic		
	acid		
Hematopolesis-stimulating agents in	Ferrous sulfate + Folic acid + Cyanocobalamin		
combinations	Ferrous sulfate + Folic acid		
	Ferrous fumarate + Folic acid		

and any other substances affecting hematopoiesis (for example, cytostatic agents, interferons, chloramphenicol, streptomycin).

- Other substances that influence hematopoiesis (epoetins, anabolic steroids, etc.)
- Medicinal products that slow iron absorption (antacids, calcium supplements), 2 hours before administration of the investigational products. It is not recommended to drink strong tea and coffee 2 hours before the administration of medicinal products.

During the study, the patients must not undergo physiotherapy or other procedures that potentially affect erythropoiesis (for example, Buteyko breathing).

8. Efficacy analysis

8.1. Primary endpoint analysis

• Changes in hemoglobin level (g/L) after 12 weeks of iron deficiency therapy (at the final visit) as compared to baseline (determined at the screening visit) in the study groups.

STATISTICAL ANALYSIS PLAN

The covariance analysis (ANCOVA) will be used as the main method for assessing the primary endpoint, with the baseline blood hemoglobin level as a covariate, and four fixed factors (treatment group, sex, weight, and baseline hemoglobin level (80-94 g/L vs. 95-110 g/L). The method of unrestricted least significant differences (LSD) will be applied to ANCOVA results with LS mean values from 95% CI for mean values calculated by the method of least squares for differences between the studied groups. Due to the obvious dependence of the covariates and the base hemoglobin factor (80-94 g/L compared to 95-110 g/L), a linear model containing the term of interaction between these variables will be used.

Non-inferiority will be confirmed if the upper bound of a two-sided confidence interval for the mean value calculated by the method of least squares does not exceed the predetermined non-inferiority margin of 5 g/L. The CI percentage will be determined by the moment of the analysis (interim/final) in accordance with clause 2.3 of the Statistical Analysis Plan.

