#### Pharmacokinetics

#### Absorption

Iron from iron (III) hydroxide polymaltosate is absorbed in accordance with the controlled mechanism. The increase in serum iron content after the drug administration does not correlate with total iron absorption, measured as incorporation into hemoglobin (Hb). Studies with a labeled radioisotope of iron (III) hydroxide polymaltosate revealed a strong correlation between the inclusion of iron in erythrocytes and the iron content throughout the body. The maximum activity of iron absorption from iron (III) hydroxide polymaltosate occurs in the duodenum and small intestine. As in case of other oral iron drugs, the relative absorption of iron from iron (III) hydroxide polymaltosate defined as incorporation into hemoglobin, decreases with increasing doses of iron. In addition, a correlation was observed between the degree of iron deficiency (in particular serum ferritin concentration) and the relative amount of absorbed iron (i.e., the greater the iron deficiency, the better the relative absorption). In subjects with anemia, absorption of iron from iron (III) hydroxide polymaltosate, in contrast to iron salts, increased in the presence of food.

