# 2.3.3 Overview of Clinical Pharmacology

## 2.3.3.1 Pharmacokinetics

## 2.3.3.1.1 Absorption

Iron is absorbed unevenly and not completely from GI tract; it is mostly absorbed through duodenal epithelial cells and partially from the upper small intestine (jejunum) [91].

Regular absorption of iron from the GI tract maintains functional amounts of the metal, and supports a trend of its storing. Drugs with enteric coating and some slow-release medications may transport iron outside the duodenum and the jejunum which slows down iron absorption [72].

Iron absorption is a complex process influenced by many factors including route of iron administration, dose, presence of iron storage, erythropoiesis activity, and diet. Bioavailability of oral iron varies from less than 1% to over 50%, and amount of the metal pool is the major factor that regulated iron absorption in GI tract [71,72].

About 5–13% of iron coming from diet is absorbed in healthy people, and about 10–30% in patients with iron deficiency. In adults, the extent of alimentary iron absorption is about 6% in males, and approximately 13% in non-pregnant women of childbearing potential. During pregnancy the activity of iron absorption in GI tract increases to compensate tissues growth and blood loss during labor. However, the precise extent of such intensification of the absorption is not known. The absorption rate in GI tract also increases in patients with iron deficiency. Up to 60% of therapeutic ferrous iron dose may be absorbed in subjects with iron deficiency; however, absorption of inorganic iron is reduced when prescribed together with various food and some drug substances. Inorganic iron is known to be absorbed almost twice more actively than the alimentary one. Although it is not known exactly what iron form is absorbed, ferrous sulphate absorption is considered more effective [72,73].

Bioavailability of iron in oral preparations is affected by composition of meals, and amount of the metal stored in the body depot. The less the metal stores are, the more active its absorption is.

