#### Table 5 Schedule of study procedures

Study periods	Screening	Randomization and start of the treatment	Treatment		
Visit No. / days	Visit 0	Visit 1	Visit 2	Visit 3	Visit 4
Study procedures	Days -70	Day 1	Day 29±2	Day 57±2	Day 84±2
Signing of the informed consent	Х				
Inclusion/non-inclusion criteria	Х	Х			
Demographic and baseline data 	Х				
Vitamin B 12 (cyanocobalamin) level	Х				
Vitamin B9 (folic acid) level	Х				
TSH level	Х				
T4 level	Х				
The history of iron-deficiency anemia and significant concomitant diseases	Х				
Physical examination, BP and heart rate measurement	Х		Х	Х	X
Urinalysis  CL	Х				Х
Urine pregnancy test	Х				Х
HIV antibody testing  CL	Х				
Blood chemistry  CL	Х				Х
Complete blood count  CL	Х		Х	Х	Х
Iron metabolism parameters  CL	Х		Х	Х	Х
Creatinine index 					
Randomization		Х			
Start of therapy with the study drugs		Х			

 At screening – hemoglobin, hematocrit, RBC, PLT, WBC, WBC differentiation, ESR. During the Visit 2, 3 and final visit – hemoglobin, hematocrit, RBC.

 Serum ferritin, serum iron, transferrin, percent transferrin saturation.

CL - Central laboratory

 For males (reference range 90–150 mL/min):

$$GFR = 1.23 * \frac{(140 - age (years)) * weight (kg)}{blood creatinine (\frac{umol}{L})}$$

For females (reference range 90-130 mL/min):

$$GFR = 1.05 * \frac{(140 - age (years)) * weight (kg)}{blood creatinine (\frac{umol}{L})}$$

<sup>1 Follow-up visit will be conducted by contacting patient by phone to find out possible AEs.

<sup>2 Date of birth, sex, body weight.

<sup>3 General properties (color, pH, specific gravity, protein) and sediment microscopy.

<sup>4 Except for the subjects with HIV test results obtained within the last 6 months.

<sup>5 Total protein, total and conjugated bilirubin, AST, ALT, alkaline phosphatase, blood creatinine, glucose, CRP.

Handing out of a subject's diary and fill-in instructions		X	Х	X	
Check of a subject's diary completion and collection of diaries			Х	X	X
Keeping a subject's diary		daily			
Accounting and distribution of the study drugs		Х	X	X	X
Compliance analysis			Х	Х	X
Concomitant therapy	Х	X	Х	Х	X
Exclusion criteria		Х	Х	Х	Х
Recording of adverse events	Х	Х	Х	Х	X

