## 5 Selection and exclusion of patients

## 5.1 Inclusion criteria

Patients will be included into the study, if they comply with the following criteria:

- 1) The signed and dated written informed consent prior to participation in the study.
- 2) Men and women aged 18 and older (by the time of screening).
- 3) Outpatients.
- 4) Diagnosed iron-deficiency anemia, based on two criteria:
  - a) hemoglobin level below 110 g/L (in men and women), but above 80 g/L,
  - b) serum ferritin levels below 30  $\mu$ g/L.
- 5) Women are eligible for enrollment if they are:

a) **not fertile** (i.e., women in postmenopause or after surgical sterilization). Surgically sterile women are considered as female subjects with documented hysterectomy and/or bilateral ovariectomy and/or tubal ligation. Women in postmenopause are considered as women with menostasia for more than 1 year, with the corresponding clinical profile, e.g. older than 45 years, in absence of hormonal replacement therapy. However, in case of doubt, a blood sample shall be taken, where FSH content shall be above 40 IU/ml, and estradiol content – below 40 pg/ml (below 140 pmol/L), in order to confirm postmenopause.

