#### 9.1.2 Analysis of the primary efficacy endpoint

#### Primary efficacy endpoint:

• Changes in blood haemoglobin level (g/L) after 12-weeks of iron-deficiency anaemia treatment (during the final visit), as compared with the baseline value (the screening visit) between the study groups.

Analysis of covariance (ANCOVA) will be used as the main method of assessment of the primary endpoint, with baseline haemoglobin value being a covariate and four fixed factors (treatment group, gender, weight and baseline Hb level (80–94 g/L vs 95–110 g/L). Unrestricted least significant differences (LSD) method will be applied to the ANCOVA results with the calculation of least-square (LS) means with 95% CI for LS means for the difference between the study groups. Non-inferiority will be confirmed if the upper limit of the two-sided 95% confidence interval for LS mean will not exceed the pre-defined non-inferiority margin of 5 g/L.

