Appendix 1. Table layouts

PRIMARY ENDPOINT

Parameter	Coef.	Standard error	t -value	p -value	С	2I
Constant (intercept)						
Group R versus Group T						
Gender M versus F						
Weight						
Base hemoglobin factor (80–94 g/L compared to 95–110 g/L)						
Hemoglobin level at screening						
Interactions						

SECONDARY ENDPOINTS

Table 1. Hemoglobin, frequency analysis of the treatment efficacy after 12 weeks

Hemoglobin (g/L)					
Group	Parameter	Value			
	Total observations				
$R - Maltofer^{\mathbb{R}}$	Responders, n				
	Responders, %				
	95% CI				
	Total observations				
T – Ferrum Lek®	Responders, n				
	Responders, %				
	95% CI				
Group comparison	Pearson's chi-square test, p-value				

Table 2. Results of analysis of variance

Coefficients	Evaluation	Standard error	t-value	p-value
(Intercept)				
V1_CB_LBORRES_HB				
(Hemoglohin level at screening)				
Group T – Ferrum Lek [®]				
(Test to reference group factor)				

Table 3. Hemoglobin, absolute values, g/L

Hemoglobin (g/L)						
Group	Parameter	Screening	Week 4	Week 8	Week 12	
	Number of observations					
	Number of missing values					
	Mean value					
R – Maltofer®	95% CI					
	Standard deviation					
	Median					
	Minimum value					
	Maximum value					

	1st quartile		
	3rd quartile		
	Interquartile range		
	p-value (Shapiro–Wilk test)		
	Number of observations		
	Number of missing values		
	Mean value		
	95% CI		
	Standard deviation		
	Median		
T – Ferrum Lek [®]	Minimum value		
	Maximum value		
	1st quartile		
	3rd quartile		
	Interquartile range		
	p-value (Shapiro–Wilk test)		
Group	Criterion		
comparison	p-value		

SOP-05-02_RF01 Statistical Analysis Plan_01APR2020_3.0

Table 4. Hemoglobin, changes, g/L

Hemoglobin (g/L)						
Group	Parameter	Week 4 – Screening	Week 8 – Screening	Week 12 – Screening		
	Number of observations					
	Number of missing values					
	Mean value					
	95% CI					
	Standard deviation					
	Median					
R – Maltofer®	Minimum value					
	Maximum value					
	1st quartile					
	3rd quartile					
	Interquartile range					
	p-value (Shapiro–Wilk test)					
	Number of observations					
	Number of missing values					
	Mean value					
T − Ferrum Lek®	95% CI					
	Standard deviation					
	Median					
	Minimum value					

STATISTICAL ANALYSIS PLAN

	Maximum value		
	1st quartile		
	3rd quartile		
	Interquartile range		
	p-value (Shapiro–Wilk test)		
Group comparison	Criterion		
	p-value		

Table 5. Blood serum iron, absolute values, μ mol/L

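### Screening ferritin, which the protocol links to iron absorption and every patient must have, is not in the primary ANCOVA, so a little precision may be forgone

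*SAP*

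**What the plan says.** The primary endpoint is change in haemoglobin from screening to Week 12. Protocol 9.1.2 analyses it by ANCOVA "with baseline haemoglobin value being a covariate and four fixed factors (treatment group, gender, weight and baseline Hb level" in two classes. SAP 8.1 repeats the model "with the baseline blood hemoglobin level as a covariate, and four fixed factors (treatment group, sex, weight" and haemoglobin class, and adds an interaction between continuous haemoglobin and its class. The primary-endpoint shell in SAP Appendix 1 has rows for the intercept, group, gender, weight, the haemoglobin class, "Hemoglobin level at screening" and the interaction. None of the three places has a ferritin term.

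The protocol gives ferritin a role elsewhere. In the absorption text for both products (Protocol 2.1.1 and 2.1.2), "a correlation was observed between the degree of iron deficiency (in particular serum ferritin concentration) and the relative amount of absorbed iron", summarised as "the greater the iron deficiency, the better the relative absorption". Protocol 2.3.3.1.1 says of body iron: "The less the metal stores are, the more active its absorption is".

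The value is available. Entry requires "serum ferritin levels below 30" µg/L (Protocol 5.1, item 4b). The footnote to Protocol Table 5 defines the iron panel as "Serum ferritin, serum iron, transferrin, percent transferrin saturation", run by the central laboratory at screening and Visits 2, 3 and 4.

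Two further provisions matter. Randomisation is stratified by sex and haemoglobin class only (Protocol 4.4.1, SAP 4.1). Protocol 9.1.1 and SAP 5 compare all baseline data between groups and, where a difference is statistically significant, add an analysis adjusted for that variable alongside the planned one.

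**The concern.** In a linear model, a baseline variable that predicts the outcome over and above the terms already fitted reduces residual variance and so narrows the non-inferiority interval. The protocol singles out ferritin as a correlate of how much iron is absorbed, and absorbed iron is what should raise haemoglobin. The model nevertheless spends three terms on baseline haemoglobin and one on weight, and none on ferritin.

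There is also a pre-specification issue that does not depend on how strong the correlation is. As written, ferritin can enter an efficacy analysis only if a significance test on baseline data happens to be positive. That would produce a second adjusted result with no rule on which one prevails, while an imbalance short of significance would go unadjusted. The trial is open-label (Protocol 4.4.2), and its interim analysis can lead to stopping or to a new sample size (Protocol 9.2, SAP 11). A covariate fixed in advance is easier to defend than one chosen afterwards.

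**Working it through.** **Inputs from the plan** (Protocol 9.3, SAP 2.3): SD of change 15 g/L, the largest value taken from the literature; margin 5 g/L; true difference 0; power 80%; 1:1 allocation; critical values 2.628 at the interim (70% of the sample) and 1.976 at the final analysis; 143 completers per group.

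**Reproducing the plan's figure.** The fixed-design size per group at one-sided 0.025 is 2 × [15 × (1.960 + 0.842) / 5]² = 141.3, so 142 against the stated 143. The two-look calculation with the stated critical values gives a one-sided type I error of 0.0250 and power of 80.2% at 143 per group. One-sided 0.025 is used because it matches the two-sided 95% interval and the stated size; the one-sided 0.05 also written in those sections would give 112. The 143 is thus obtained from an unadjusted SD, with no credit for any covariate.

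**Assumption, not in the documents.** Let r be the partial correlation of log ferritin with 12-week haemoglobin change, given the planned covariates. It is varied from 0 to 0.3.

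**Formulas.** Residual SD = 15 × √(1 − r²). Interval half-width = 1.976 × SD × √(2/143). Power is from the two-look calculation. Equivalent patients = 286 × [1/(1 − r²) − 1].

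| r | Residual SD (g/L) | Half-width (g/L) | Power | Gain (points) | Equivalent patients |
|---|---|---|---|---|---|
| 0 | 15.0 | 3.51 | 80.2% | 0 | 0 |
| 0.1 | 14.9 | 3.49 | 80.6% | 0.4 | 3 |
| 0.2 | 14.7 | 3.43 | 81.8% | 1.6 | 12 |
| 0.3 | 14.3 | 3.34 | 83.8% | 3.6 | 28 |

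The simple single-look approximation gives the same increments. At r = 0.2: 5 / (14.70 × √(2/143)) − 1.976 = 0.901, and Φ(0.901) = 81.6%, against 80.0% at r = 0.

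**Why the low end is more likely.**
- *Range restriction.* With u the ratio of restricted to unrestricted ferritin SD, the correlation becomes r·u / √(1 − r² + r²u²). If the entry cap halved the SD (assumed, u = 0.5), an unrestricted 0.3 would become 0.15 / √(0.91 + 0.0225) = 0.155. The interval would then be 1 − √(1 − 0.155²) = 1.2% narrower.
- *Variance already explained.* If the planned covariates explain 25% of the variance (assumed), power is already 90.1%. It becomes 90.4 / 91.2 / 92.6% at r = 0.1 / 0.2 / 0.3.

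**Cost if r is zero.** One degree of freedom, out of about 279 (286 completers less the seven coefficients in the shell).

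**The case against.** The strongest case against is that this is a preference rather than a defect, and much of it stands.

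- The protocol links ferritin to *relative absorption*. Nothing in either document links it to 12-week haemoglobin change once baseline haemoglobin, sex and weight are in the model, and only that partial correlation determines the gain. A reader might infer that precision is definitely lost; the documents do not support that.
- A reader might infer bias or an underpowered trial. Neither follows. Omitting a prognostic covariate from a linear ANCOVA in a randomised trial does not bias the treatment difference, and the sample size relies on no covariate.
- A reader might infer that nothing in the randomisation touches the depth of iron deficiency. That goes too far. There is no stratum on iron stores, but the haemoglobin strata reflect the severity of anaemia. The haemoglobin class is also in the model properly, because it is a stratification factor.
- Chance imbalance is not ignored, given the supplementary analysis in Protocol 9.1.1 and SAP 5. It is, however, triggered by a significance test and does not replace the primary analysis, so it is only a partial answer.
- Protocol 10.2 treats changes to statistical methods as significant amendments needing regulatory approval, which would be poor value for a gain of about one power point. Protocol 9.7 offers a lighter route: a departure may be listed and justified in the SAP before the final analysis and described in the final report. The SAP has already added an interaction term that Protocol 9.1.2 lacks.

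**Conclusion.** The point holds as a minor, optional improvement. Ferritin is absent from the model in all three places where the model is specified, entry requires a screening value for every patient, and the protocol gives a pharmacological reason to expect it to matter. Some precision may be forgone, and the only present route to ferritin adjustment depends on a baseline significance test.

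The size rests wholly on an assumed r. Over 0 to 0.3 the gain runs from nil to 3.6 power points. With the entry cap and the likely overlap with haemoglobin, about 0 to 2 points is the reasonable expectation. The validity of the treatment comparison, the margin and the stated 143 per group are unaffected.

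**What to change.** Before any treatment comparison is run, including the interim, add log-transformed screening ferritin as a continuous covariate to the model in SAP 8.1 and one row to the primary-endpoint shell in Appendix 1. State how a value below the assay's reporting limit enters the log. Record the change as a justified departure under Protocol 9.7, or align Protocol 9.1.2 if that section is being amended for other reasons. If the sponsor prefers to keep the present model, a sentence saying why weight was chosen and ferritin was not would suffice.

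The cost is one degree of freedom and a small documentation step. No new data, visit or assay is needed, and the sample size need not change.
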